8.3 Definitions of analysis sets

8.3.1 Full analysis set

The full analysis set is defined as all patients enrolled who received at least one dose of investigational product.

Safety data summaries and analyses will be produced based on the full analysis set.

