8.3.2 Evaluable for response analysis set

The evaluable for response analysis set will be all patients who have received at least one dose of treatment and have measurable disease at baseline according to the independent review of baseline imaging data.

The primary analysis of ORR, and other RECIST-based outcomes by independent central review will be produced based on the evaluable for response analysis set. All other efficacy variables will be summarised using the full analysis set.

To support the primary analysis, demographic data will also be summarised for the evaluable for response analysis set

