8.9 Methods for statistical analyses

All data will be presented for the overall full analysis set/evaluable for response set (as appropriate), and also by two cohorts defined by line of treatment; TKI treatment only / previous TKI and a platinum-based doublet chemotherapy (patients may have also received additional lines of treatment).

Descriptive statistics will be used for all variables, as appropriate. Continuous variables will be summarised by the number of observations, mean, standard deviation, median, minimum, and maximum. Categorical variables will be summarised by frequency counts and percentages for each category. Unless otherwise stated, percentages will be calculated out of the full analysis set.

Baseline will be the last assessment of the variable under consideration prior to the intake of the first dose of investigational product, except for efficacy variables. For efficacy variables, baseline is defined as the last visit prior to enrolment.

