8.9.1 Analysis of the primary variable(s)

Objective response rate (ORR) by ICR in the evaluable for response analysis set will be presented together with 95% exact (Clopper Pearson) confidence intervals. Summaries of the number of patients with best response in each of the follow categories will be summarised: Complete Response (CR), Partial Response (PR), Stable Disease (SD), Progressive Disease (PD) and Non-Evaluable (NE).

The baseline patient characteristics will be summarised, including demographics, EGFR mutation type and prior anti-cancer therapy, including most recent previous treatment.

Additional summaries of ORR will be performed

- ORR by investigator assessment
- ORR summarised for both confirmed and unconfirmed responses
- ORR by EGFR mutation subtype: Exon 19 deletion/L858R/Other.
- ORR in the subgroup of patients who received TKI as last treatment prior to study start and those whose treatment prior to study start was not a TKI
- ORR at week 6 and 12 will also be summarised.

The concordance between ORR as assessed by ICR and by investigator will be presented.

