8.9.5 Sensitivity analysis

The same methods of analysis will be applied to analyse ORR, DoR, DCR and PFS based on the RECIST data assessed by the investigator.

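### The investigator sensitivity analysis of ORR appears to change reader and population together, and no ICR ORR over all treated patients is planned

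*Supplement*

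**What the plan says.** Section 8.3.1 makes the full analysis set an all-treated set: "The full analysis set is defined as all patients enrolled who received at least one dose of investigational product". Section 8.3.2 defines the evaluable-for-response set as patients who were dosed and who "have measurable disease at baseline according to the independent review of baseline imaging data". It then assigns endpoints to sets in two consecutive sentences: "The primary analysis of ORR, and other RECIST-based outcomes by independent central review will be produced based on the evaluable for response analysis set", followed by "All other efficacy variables will be summarised using the full analysis set". Section 8.9 adds that, unless otherwise stated, "percentages will be calculated out of the full analysis set".

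For the primary endpoint, section 8.9.1 reads: "Objective response rate (ORR) by ICR in the evaluable for response analysis set will be presented together with 95% exact (Clopper Pearson) confidence intervals". The additional ORR summaries listed there are by investigator assessment, by confirmed and unconfirmed response, by EGFR mutation subtype, by whether the last prior treatment was a TKI, and at weeks 6 and 12. On agreement between readers it says only: "The concordance between ORR as assessed by ICR and by investigator will be presented". Section 8.9.5 gives the sensitivity analysis in one sentence: "The same methods of analysis will be applied to analyse ORR, DoR, DCR and PFS based on the RECIST data assessed by the investigator". Amendments 1 and 2 leave sections 8.3.2, 8.9.1 and 8.9.5 as they were.

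**The concern.** The objectives name the investigator-based ORR as the sensitivity analysis of the primary ORR. Its purpose is to show how far the result depends on who reads the scans, so it should hold the patients fixed and change the reader. If the ICR ORR is over ICR-measurable patients and the investigator ORR is over all treated patients, a gap between them may be reader disagreement, the extra patients, or both. Agreement could also be two effects cancelling.

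The second issue is the denominator. Patients enter because the site found a measurable lesion (inclusion criterion 9). Section 5.1.2 says ICR results are not passed to investigators, so the central read does not gate enrolment. It can only drop treated patients from the primary denominator. In a single-arm trial whose main result is one proportion, a reader should be able to see what that removal is worth.

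**Working it through.** **1. Which set does each analysis use?**

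- ICR ORR, DoR and DCR: evaluable-for-response set (8.3.2; repeated for ORR in 8.9.1).
- Investigator ORR, DoR and DCR: not ICR outcomes, so they fall under the residual sentence of 8.3.2, which gives the full analysis set. The default denominator in 8.9 agrees.
- Section 8.9.5 carries over methods and names no set.
- Section 8.4 restricts ORR to patients with measurable disease without saying whose reading counts outside the primary analysis. Because criterion 9 requires a measurable lesion at entry, the investigator-measurable patients are nearly the whole full analysis set. Section 8.4 therefore does not lead back to the ICR-evaluable set.
- Concordance: no population stated.
- ICR ORR in the full analysis set: not among the summaries in 8.9.1.

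**2. The plan's own precision figure.** Section 8.2 gives 33.0% to 47.4% for an ORR of 40% with 175 patients. The Wilson interval for 70/175 is 33.03% to 47.40%, which reproduces it. The planned Clopper-Pearson interval is 32.68% to 47.66%, still within ±8 points. Both use all 175 patients and make no allowance for patients the ICR finds non-measurable.

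**3. Direction.** Section 5.1.1 applies the Appendix D criteria to both readers. In Appendix D Table 4, a patient without target lesions has no route to PR, so counting such patients as non-responders is the natural all-treated rule. With *r* the evaluable-set ORR and *f* the excluded share:

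all-treated ICR ORR = *r* × (1 − *f*); excess of the evaluable-set rate = *r* × *f* ≥ 0.

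**4. Size.** Inputs: N = 175 and ORR 40% (8.2); ORR 50%, the phase I T790M+ rate (1.3). The share *f* is not in the documents; 2% to 15% is assumed. Counts are rounded to whole patients, intervals are Clopper-Pearson, and differences are taken before rounding.

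| Excluded | Evaluable-set ORR | All-treated ICR ORR (95% CI) | Excess, points |
|---|---|---|---|
| 4 (2%) | 68/171 = 39.8% | 68/175 = 38.9% (31.6–46.5) | 0.9 |
| 9 (5%) | 66/166 = 39.8% | 66/175 = 37.7% (30.5–45.3) | 2.0 |
| 18 (10%) | 63/157 = 40.1% | 63/175 = 36.0% (28.9–43.6) | 4.1 |
| 26 (15%) | 60/149 = 40.3% | 60/175 = 34.3% (27.3–41.8) | 6.0 |
| 4 (2%) | 86/171 = 50.3% | 86/175 = 49.1% (41.5–56.8) | 1.1 |
| 9 (5%) | 83/166 = 50.0% | 83/175 = 47.4% (39.8–55.1) | 2.6 |
| 18 (10%) | 78/157 = 49.7% | 78/175 = 44.6% (37.1–52.3) | 5.1 |
| 26 (15%) | 74/149 = 49.7% | 74/175 = 42.3% (34.9–50.0) | 7.4 |

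**5. How far the set alone can move the investigator result.** Suppose the two readers agree on every evaluable patient. The investigator ORR then shifts by *f* × (*r*_excl − *r*), where *r*_excl is the investigator response rate in the excluded patients. At an ORR of about 40%, the bounds *r*_excl = 0 and 1 give:

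- 4 excluded: 68/175 = 38.9% to 72/175 = 41.1%, a shift of −0.9 to +1.4 points.
- 26 excluded: 60/175 = 34.3% to 86/175 = 49.1%, a shift of about −6 to +9 points.

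These are outer bounds, not expected values.

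**6. Precision after exclusion.** With 157 evaluable patients (10% excluded) and ORR about 40%, the exact interval for 63/157 is 32.4% to 48.2%. Its upper half-width is 8.1 points, just outside the stated ±8.

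**The case against.** No sentence puts investigator ORR in the full analysis set in so many words. Section 8.4 ties ORR to measurable disease, 8.9.5 carries over the same methods, and 8.9 presents data for either set as appropriate. A concordance table is also normally built on the same patients under both readers. This stands in part: the set for investigator ORR is an inference from a default rule, and someone who takes the plan to assign it expressly goes too far. But 8.3.2 is where sets are assigned, and its residual sentence points to the full analysis set.

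A reader might also infer that the primary denominator is shaped by outcome. The documents do not support that. Membership depends on dosing and baseline imaging only, the radiologists are blinded to individual patient data, and no post-baseline scan is required, so early dropouts stay in. Nor do the documents say when the baseline central read is made. Restricting response rate to measurable disease is conventional and is prespecified here.

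The effect may be small. Criterion 9 is strict, and the ICR receives radiotherapy and biopsy information for choosing target lesions, so an excluded share near 2% is plausible.

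Two further arguments carry less weight. The supplement contains no SAP, and one could add these tables; but the protocol itself assigns the sets and lists the ORR summaries. The all-treated rate could be worked out by hand from the responder count and the set sizes; that is not the same as a prespecified result with an interval.

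**Conclusion.** The point holds as a modest, inexpensive improvement. On the most natural reading of 8.3.2, supported by 8.9, the investigator sensitivity analysis differs from the primary in both reader and population, and neither 8.9.5 nor the concordance summary settles the set. The absence of an all-treated ICR ORR is plain from 8.3.2 and 8.9.1.

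With non-measurable patients counted as non-responders, the evaluable-set ORR can only equal or exceed the all-treated ICR ORR. The excess is 0.9 to 6.0 points at 40% and 1.1 to 7.4 points at 50%, if 2% to 15% of 175 treated patients are not ICR-measurable. That share is an assumption. At 2% the matter is negligible; at 10% it is 4 to 5 points, against a stated precision of ±8. None of this makes the primary analysis invalid.

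**What to change.** (a) In 8.3.2 and 8.9.5, state that the investigator ORR, DoR and DCR sensitivity analyses and the ICR–investigator concordance table use the evaluable-for-response set, the same patients as the primary analysis. Keep the full-analysis-set version of the investigator results as supplementary.

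(b) In 8.9.1, add a sensitivity analysis of confirmed ICR ORR in the full analysis set with an exact 95% confidence interval, counting patients without ICR-measurable baseline disease as non-responders.

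Reader and population then change one at a time. The cost is some wording and a few extra tables, with no new data. The supplementary all-treated ORR will be somewhat lower than the headline whenever any responder is observed and any patient is excluded. The primary analysis stays as it is.

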8.3.3 PK analysis set

Patients in the Full Analysis Set who have at least one measurable PK concentration, supported by the relevant date and time of this sample and for each time a PK sample was taken the dosing data for that day; and for samples taken after multiple dosing the dosing data for the 2 days prior to the sample day as well as the sample day. For any individual sample to be included in the PK analysis set the full sample data and dosing data needs to be present for that sample.

8.3.4 QTc analysis set

Patients in the Full Analysis Set who have at least one evaluable QT/QTc interval value at a scheduled post-dose/time matched to screening time point.

8.4 Outcome measures for analyses

Independent Central Review of RECIST based assessments

The Independent Central Review of all radiological imaging data will be carried out using RECIST version 1.1. All radiological scans for all patients (including those at unscheduled visits, or outside visit windows) will be provided to the ICR. Prior radiotherapy reports for patients (at baseline) and information on biopsied lesions will also be provided to the ICR to allow the selection of appropriate target lesions. The imaging scans will be reviewed by two independent radiologists using RECIST 1.1 criteria and will be adjudicated if required. For each patient, the ICR will define the overall visit response data (CR, PR, SD, PD or NE) and the relevant scan dates for each time point (i.e. for visits where response or progression is/is not identified). If a patient has had a tumour assessment which cannot be evaluated then the patient will be assigned a visit response of not evaluable (NE) (unless there is evidence of progression in which case the response will be assigned as PD). Endpoints (ORR, DoR, DCR, PFS) will be derived from the overall visit response date and the scan dates. ORR will only include patients whose response has been confirmed by a second scan at least 4 weeks after the initial response. The endpoint of tumour shrinkage will be assessed from tumour size measurements based on the primary independent radiologist assessment.

Further details of the Independent Central Review will be documented in the Independent Review Charter.

Investigator RECIST based assessments

From the investigators review of the imaging scans, the RECIST tumour response data will be used to determine each subject's visit response according to RECIST version 1.1.

At each visit, patients will be programmatically assigned a RECIST 1.1 visit response of CR, PR, SD or PD depending on the status of their disease compared with baseline and previous assessments. If a patient has had a tumour assessment which cannot be evaluated then the patient will be assigned a visit response of not evaluable (NE) (unless there is evidence of progression in which case the response will be assigned as PD).

Please refer to [Appendix D](#) for the definitions of CR, PR, SD and PD.

Overall Response Rate (ORR)

ORR rate is defined as the number (%) of subjects with measurable disease with at least one visit response of CR or PR that is confirmed at least 4 weeks later (according to ICR for the primary analysis). Data obtained up until progression, or last evaluable assessment in the absence of progression, will be included in the assessment of RR. However, any complete response or partial response which occurred after a further anticancer therapy was received will not be included in numerator of the ORR calculation.

In the case where a subject has two non-consecutive visit responses of PR, then, as long as the time between the 2 visits of PR is greater than 4 weeks and there is no PD between the PR visits, the subject will be defined as a responder. Similarly, if a subject has visit responses of CR, NE, CR, then, as long as the time between the 2 visits of CR is greater than 4 weeks, then a best response of CR will be assigned.

Duration of Response (DoR)

Duration of response will be defined as the time from the date of first documented response, (that is subsequently confirmed) until date of documented progression or death in the absence of disease progression, the end of response should coincide with the date of progression or death from any cause used for the PFS endpoint. The time of the initial response will be defined as the latest of the dates contributing towards the first visit response of PR or CR. If the response is not confirmed, it will not be included.

If a subject does not progress following a response, then their duration of response will use the PFS censoring time.

Disease control rate (DCR)

Disease control rate is defined as the percentage of patients who have a BoR of CR or PR or SD.

Tumour Shrinkage

Tumour shrinkage will be assessed using RECIST tumour response. The absolute change and percentage change from baseline in sum of tumour size at each assessment will be calculated. The best change in tumour size will include all assessments prior to progression or start of subsequent anti-cancer therapy.

Progression Free Survival (PFS)

PFS is defined as the time from enrolment until the date of objective disease progression or death (by any cause in the absence of progression) regardless of whether the patient withdraws from study therapy or receives another anti-cancer therapy prior to progression. Patients who have not progressed or died at the time of analysis will be censored at the time of the latest date of assessment from their last evaluable RECIST assessment.

However, if the patient progresses or dies after three or more missed RECIST assessments visits, the patient will be censored at the time of the latest evaluable RECIST assessment. If the patient has no evaluable visits or does not have baseline data they will be censored at 0 days unless they die within two visits of baseline.

The PFS time will always be derived based on scan/assessment dates not visit dates.

RECIST assessments/scans contributing towards a particular visit may be performed on different dates. The following rules will be applied

- Date of progression will be determined based on the earliest of the dates of the component that triggered the progression

- When censoring a patient for PFS the patient will be censored at the latest of the dates contributing to a particular overall visit assessment

Overall Survival

Overall survival is defined as the time from the date of first dose until death due to any cause. Any patient not known to have died at the time of analysis will be censored based on the last recorded date on which the patient was known to be alive.

Note: Survival calls will be made in the 2 weeks following the date of the final data cut-off for the analysis, and if patients are confirmed to be alive (if the death date is post the final data cut-off date) these patients will be censored in the analyses as of the date of the final data cut off.

HRQoL & Symptoms

Patient reported outcomes will be assessed using the EORTC QLQ-C30 and QLQ LC13 questionnaires. The QLQ-C30 consists of 30 questions which can be combined to produce 5 functional scales (Physical, Role, Cognitive, Emotional, Social), 3 symptom scales (Fatigue, Pain, Nausea/vomiting), 5 individual items (dyspnoea, insomnia, appetite loss, constipation, diarrhoea) and a global measure of health status. The QLQ LC13 is a lung cancer specific module comprising 13 questions to assess lung cancer symptoms (cough, haemoptysis, dyspnoea and site-specific pain), treatment related side-effects (sore mouth, dysphagia, peripheral neuropathy and alopecia) and pain medication. With the exception of a multi-item scale for dyspnoea, all are single items.

An outcome variable consisting of a score from 0 to 100 will be derived for each of the symptom scales/symptom items, the functional scales and the global health status scale in the QLQ-C30 and for each of the symptom scales/items in the QLQ LC13 according to the EORTC QLQ-C30 Scoring Manual and EORTC QLQ LC13 instructions.

Higher scores on the global health status and functioning scales indicate better health status/function. Higher scores on the symptoms scales indicate greater symptom burden.

The primary PRO outcome measures will be patient-reported lung cancer symptoms assessed using the EORTC QLQ LC13, namely

- dyspnoea (multi-item scale based on 3 questions: were you short of breath when you rested; walked; climbed stairs)
- cough: 1 item (how much did you cough?)
- haemoptysis: 1 item (did you cough up blood?)
- pain: 3 individual items (Have you had pain in your chest; your arm or shoulder; other parts of your body?)

Definition of clinically meaningful changes

Changes in score compared to baseline will be evaluated. A minimum clinically meaningful change is defined as a change in the score from baseline of ≥ 5 for scales/items from the QLQ LC13 and ≥ 10 for scales/items from the QLQ-C30 (Obosa et al 1998).

For example, a clinically meaningful deterioration or worsening in chest pain (as assessed by QLQ LC13) is defined as an increase in the score from baseline of ≥ 5 . A clinically meaningful improvement in fatigue (as assessed by QLQ-C30) is defined as a decrease in the score from baseline of ≥ 10 .

At each post-baseline assessment, change in symptoms/functioning from baseline will be categorised as improved, stable or worsening as shown in Table 10.

Table 10 Visit Response for HRQoL and disease-related symptoms

Score	Change from baseline	Visit Response
LC13 symptom scales/items	$\geq +5$	Worsened
	≤ -5	Improved
	Otherwise	Stable
C30 symptom scales/items	$\geq +10$	Worsened
	≤ -10	Improved
	Otherwise	Stable
C30 functional scales and Global health status	$\geq +10$	Improved
	≤ -10	Worsened
	Otherwise	Stable

Time to symptom deterioration

For each of the symptoms scales/items in QLQ LC13, time to symptom deterioration will be defined as the time from enrolment until the date of first clinically meaningful symptom deterioration (an increase in the score from baseline of ≥ 5) or death (by any cause) in the absence of a clinically meaningful symptom deterioration, regardless of whether the patient withdraws from study therapy or receives another anticancer therapy prior to symptom deterioration. Death will be included as an event only if the death occurs within two visits of the last PRO assessment where the symptom change could be evaluated.

Patients whose symptoms (as measured by QLQ LC13) have not shown a clinically meaningful deterioration and who are alive at the time of the analysis will be censored at the time of their last PRO assessment where the symptom could be evaluated. Also, if symptoms progress after two or more missed PRO assessments or the patient dies after two or more missed PRO assessments, the patient will be censored at the time of the last PRO assessment where the symptom could be evaluated. If a patient has no evaluable assessments or does not have baseline data they will be censored at day 1. The population for analysis of time to symptom deterioration will include a subset of the FAS population who have baseline scores ≤ 95 .

Symptom Improvement Rate

The symptom improvement rate will be defined as the number (%) of patients with two assessments at least 18 days apart (i.e. 21 days allowing a visit window of 3 days) which showed a clinically meaningful improvement (a decrease from baseline score >5 for LC13 scales/items or >10 for C30 scales/items) in that symptom from baseline. The denominator will consist of a subset of the FAS population who have a baseline symptom score ≥ 5 (LC13 scales/items) or ≥ 10 (C30 scales/items).

Time from enrolment to second progression (PFS2) (exploratory)

Time from enrolment to second progression (PFS2) is defined as the time from the date of enrolment to the earliest date of the progression event subsequent to that used for the primary variable PFS or death. The date of second progression will be recorded by the Investigator and defined according to local standard clinical practice and may involve any of; objective radiological or symptomatic progression or death. Patients alive and for whom a second disease progression has not been observed should be censored at the last time known to be alive and without a second disease progression, i.e. censored at the last progression assessment date if the patient has not had a second progression or death).

Time to second subsequent anti-cancer therapy or death is defined as the time from the date of enrolment to the earlier of the date of second subsequent anti-cancer therapy start date, or death date. Any patient not known to have had a further second subsequent therapy or death will be censored at the last known time to have not received second subsequent chemotherapy.

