8.9.2 Analysis of the secondary variable(s)

Duration of response

Duration of response in responding patients will be summarised and the number (%) of responding patients with a duration of response >3; >6; >9; >12 months will be presented. A

Kaplan Meier plot and median duration of response with 95% CI (calculated from the Kaplan Meier plot) will be presented. DCR will be summarised. DoR and DCR will be presented based on the ICR, and as a sensitivity analysis they will be present based on the investigator assessment.

Tumour shrinkage

The best absolute change in target lesion tumour size from baseline and percentage change in target lesion tumour size from baseline will be summarized using descriptive statistics and presented at each timepoint.

Tumour size will also be presented graphically using waterfall plots, to present each patient's best percentage change in tumour size as a separate bar, with the bars ordered from the largest increase to the largest decrease. Reference lines at the +20% and -30% change in tumour size levels will be added to the plots, which correspond with the definitions of progression and 'complete or partial' response respectively.

The mean and median best change from baseline in tumour size will be summarized. This will also be summarised for week 6 and week 12 data.

To assess the depth of tumour shrinkage, the proportion of patients who achieve >30%, >50% and >75% reduction in target lesions will be summarised descriptively.

Tumour shrinkage will be presented based on the primary reader ICR data, and as a sensitivity analysis they will be present based on the investigator assessment.

Progression Free Survival (PFS)

PFS will be displayed using a Kaplan-Meier plot. The number events, median (calculated from the Kaplan Meier plot), and the proportion of patients without an event at 6, 12 and 18 months summarised. PFS will be presented based on the ICR assessments, and as a sensitivity analysis PFS will be presented based on the investigator assessment.

Overall Survival (OS)

When there is sufficient data (>20 events), OS will be displayed using a Kaplan-Meier plot. The number events, median (calculated from the Kaplan Meier plot), and the proportion of patients without an event at 6, 12 and 18 months will be summarised.

As appropriate, summaries of the number and percentage of patients who have died, are still in survival follow-up, are lost to follow-up and have withdrawn consent will be presented.

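### Best tumour change stops short of the progression scan (Section 8.4), so first-scan progressors have no value and the waterfall planned in Section 8.9.2 cannot be drawn as described

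*Supplement*

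**What the plan says.** Tumour shrinkage by independent central review (ICR) is a named secondary efficacy outcome (Section 2.2).

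- **Derivation (Section 8.4, Tumour Shrinkage).** "The absolute change and percentage change from baseline in sum of tumour size at each assessment will be calculated". The next sentence limits best change: "The best change in tumour size will include all assessments prior to progression or start of subsequent anti-cancer therapy". Amendment 2 revises other parts of Section 8.4 (PFS, time to symptom deterioration, PFS2). Neither amendment touches this rule.
- **Presentation (Section 8.9.2, Tumour shrinkage).** Mean and median best change are summarised, as are the proportions with more than 30%, 50% and 75% reduction. The waterfall gives every patient a bar for best percentage change, "with the bars ordered from the largest increase to the largest decrease". Reference lines at +20% and -30% are said to match the definitions of progression and response.
- **Scan schedule (Sections 5.1.1 and 4.2).** Scans are taken every 6 weeks until objective progression. Patients treated beyond progression have no further study RECIST assessments.
- **Target-lesion progression (Appendix D, Table 2).** The sum of diameters must rise by at least 20% and by at least 5 mm over the smallest sum on study, which may be the baseline sum.

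**The concern.** The scan that shows progression is not prior to progression. For most patients this matters little, because earlier scans supply a best change. A patient who progresses at the first post-baseline scan has only that scan, and Section 8.4 gives no fallback value. Whether such a patient appears in the best-change summaries then depends on outcome, and those left out are among the poorest outcomes in the study.

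In a single-arm trial the waterfall and the average best change are read as support for the response rate, and there is no control arm in which the same exclusion would operate. A programmer following Section 8.4 would produce a plot whose right-hand tail of increases is missing, and a mean and median calculated without those patients.

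**Working it through.** No figure in the documents depends on this rule, so there is nothing to reproduce. The check sets the two sections side by side and then sizes the effect under stated assumptions.

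**1. Who loses a value?** For a patient with at least one post-baseline scan before progression, a target-lesion progression scan cannot be the best change, because it lies above the smallest sum by definition; dropping it changes nothing. For a patient with progression at the first post-baseline scan, no eligible scan remains. Any later scan would fall after progression and is excluded as well.

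**2. Can the planned +20% line be reached?** Let B be the baseline sum and S the first post-baseline sum, with progression judged on the same measurements that are plotted. Target-lesion progression requires S - B ≥ 0.20B and S - B ≥ 5 mm. A first scan that is not progression, yet shows +20% or more, must satisfy

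0.20B ≤ S - B < 5 mm, hence B < 5 / 0.20 = 25 mm.

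For B of 25 mm or more, any rise of 20% is also a rise of at least 5 mm, so it is progression and is excluded. Under Section 8.4 as written, bars at or above the line come only from patients with a baseline sum under 25 mm. The line that Section 8.9.2 ties to progression would be nearly empty.

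**3. How many bars, and how far could the mean move?** The protocol gives no rate of first-scan progression; 3% to 20% is assumed, with N = 175 (Section 8.2). Bars lost: d = 175 × rate. If all patients were counted, the mean best change would differ from the reported mean by

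d / 175 × (mean in those dropped - mean in the rest).

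Take an assumed mean of -45% in the rest. For those dropped, take either 0% (a mix of target-lesion progression with new or non-target lesion progression) or +25% (nearly all target-lesion progression).

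| Assumed first-scan PD | d | Shift if dropped mean is 0% | Shift if dropped mean is +25% |
|---|---|---|---|
| 3% | 5 | 5 × 45 / 175 = 1.3 points | 5 × 70 / 175 = 2.0 points |
| 5% | 9 | 9 × 45 / 175 = 2.3 | 9 × 70 / 175 = 3.6 |
| 10% | 18 | 18 × 45 / 175 = 4.6 | 18 × 70 / 175 = 7.2 |
| 20% | 35 | 35 × 45 / 175 = 9.0 | 35 × 70 / 175 = 14.0 |

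At 10% and +25%, for example, the mean over all patients is (-45 × 157 + 25 × 18) / 175 = -37.8%, against a reported -45%.

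**4. What does not move?** ORR is derived from overall visit responses, and Section 8.3.2 keeps every dosed patient with measurable disease at baseline in its set, so first-scan progressors count as non-responders.

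**The case against.** The other side has good arguments, and several limit the point.

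- **Section 8.9.2 may show the intent.** A bar for each patient and a +20% line suggest that progressors were meant to appear, so the exclusion is not a settled plan. That is fair. But Section 8.4 is the derivation rule, and it does not yield the display that Section 8.9.2 describes. The two need reconciling either way.
- **The SAP is not shown.** Section 8.1 promises one, and handling of patients with no usable scan is often placed there. That would excuse silence; here the protocol states a window, and it conflicts with the display.
- **Early progression is visible elsewhere.** Change is calculated at each assessment, week 6 and week 12 summaries are planned, and the cut at progression is stated only for best change. Best response still tabulates PD and NE (Section 8.9.1). This stands.
- **Not every first-scan progressor has growing target lesions.** New or non-target lesions can define progression while target lesions shrink (Appendix D, Table 4). This stands, and is why step 3 carries a 0% column.

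Two stronger readings are tempting. A reader might infer that the proportions with more than 30%, 50% and 75% reduction are inflated too. Section 8.3.2 assigns ICR RECIST outcomes to the evaluable-for-response set, and Section 8.9 otherwise defaults percentages to the full analysis set. Nothing removes patients without a best change from those denominators.

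A reader might also infer that shrinkage is plotted from a reader whom adjudication has overruled, since "The endpoint of tumour shrinkage will be assessed from tumour size measurements based on the primary independent radiologist assessment" while response follows two readers with adjudication if required. The documents do not say that adjudication selects one reader, and they leave the details to a review charter that is not shown. Use of the primary reader is prespecified and stated twice. Some mismatch with ORR is inherent anyway, because ORR requires confirmation and draws on non-target and new lesions.

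**Conclusion.** The best-change rule in Section 8.4 is wrong as written: it contradicts Section 8.9.2 and, followed literally, omits first-scan progressors from the mean and median best change and from the waterfall. The contradiction rests on the text and on the 25 mm bound. That bound assumes progression is judged on the same measurements that are plotted.

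The size is uncertain because the protocol gives no first-scan progression rate. At the assumed 3% to 20%, 5 to 35 of 175 bars are lost and the mean best change looks better by roughly 1 to 14 points. The upper end needs both a high rate and target-lesion growth in nearly all of those patients.

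The consequence is confined to a descriptive secondary endpoint with no test attached. The primary ORR, its denominator and its confidence interval are unaffected. The depth-of-response proportions are unaffected provided that the stated analysis set is kept as denominator.

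**What to change.** In Section 8.4, replace the window for best change with: *all assessments up to and including progression, and before any subsequent anti-cancer therapy*. In Section 8.9.2, state that all evaluable patients stay in the denominators of the more than 30%, 50% and 75% proportions, and report beside the waterfall the number with no post-baseline target-lesion measurement.

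The cost is a phrase in one section and a sentence in another; the measurements are already collected. The shrinkage summaries may look slightly less favourable, though not certainly so, since a progression scan triggered by a new or non-target lesion can carry the smallest target sum.
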